### **9.3.1 Safety Definitions**

#### **Adverse Event**

Any untoward medical occurrence, unintended disease or injury or any untoward clinical signs (including an abnormal laboratory finding) in subjects, users or other persons whether or not related to the IMD.

This includes events related to the IMD or the comparator. This includes events related to the procedures involved (any procedure in the clinical investigation plan). For users or other persons this is restricted to events related to the IMD.

An AE can therefore be any unfavorable and unintended sign (including an abnormal laboratory finding), symptom, or disease temporally associated with the use of IMD, whether or not it is related to the IMD. This includes an exacerbation of pre-existing conditions or events, intercurrent illnesses, or the significant worsening of the indication under investigation that is not recorded elsewhere in the eCRF under specific efficacy assessments. Anticipated fluctuations of pre-existing conditions, including the disease under study that do not represent a clinically significant exacerbation or worsening need not be considered AEs.

#### **Adverse Device Effect**

Adverse event related to the use of an IMD.

This includes any AE resulting from insufficiencies or inadequacies in the Instructions for Use, the deployment, the implantation, the installation, the operation, or any malfunction of the IMD. This includes any event that is a result of a use error or intentional misuse.

#### **Device Deficiency**

Inadequacy of a medical device related to its identity, quality, durability, reliability, safety or performance, such as malfunction, misuse or use error and inadequate labeling.

All DDs related to the identity, quality, durability, reliability, safety or performance of an IMD shall be documented throughout the clinical investigation and appropriately managed by the sponsor.

Device deficiencies that did not lead to an AE but could have led to a medical occurrence:

- If either suitable action had not been taken,
- If intervention had not been made, or
- If circumstances had been less fortunate, shall be reported to regulatory authorities and ethic committees, as required by the national regulations.

---

## Serious Adverse Event

An SAE is any untoward medical occurrence or effect that:

- Led to death, or
- Led to serious deterioration in the health of the subject, that either resulted in:
  - a life-threatening illness or injury, or
  - a permanent impairment of a body structure or a body function, or
  - in-patient or prolonged hospitalization, or
  - medical or surgical intervention to prevent life-threatening illness or injury or permanent, or
  - impairment to a body structure or a body function.
- Led to fetal distress, fetal death, or a congenital abnormality or birth defect.

This includes DDs that might have led to an SAE:

- if suitable action had not been taken, or
- if intervention had not been made, or
- if circumstances had been less fortunate.

These are handled under the SAE reporting system.

Planned hospitalization for a pre-existing condition, or a procedure required by the protocol, without a serious deterioration in health, is not considered an SAE. Important medical reactions that may not be immediately life-threatening or result in death or hospitalization but may jeopardize the subject or may require intervention to prevent one of the other outcomes listed in the definition above should also be considered serious.

The term “life-threatening”, in the definition, refers to an event in which the subject is at risk of death at the time of the event; it does not refer to an event which hypothetically might have caused death if it would have been more severe.

In addition, medical and scientific judgement is required to decide if prompt notification is required in situations other than those defined for SAEs above. This may include any event that the investigator regards as serious that did not strictly meet the criteria above but may have jeopardized the subject or required intervention to prevent one of the outcomes listed above, or that would suggest any significant hazard, contraindication, side effect, or precaution that may be associated with the use of the investigational product.

## Serious Adverse Device Effect

An adverse device effect (ADE) that has resulted in any of the consequences characteristic of an SAE.

## Unanticipated Serious Adverse Device Effect

Serious ADE which by its nature, incidence, severity or outcome has not been identified in the current version of the MAR-CUTIS risk analysis report or Instructions for Use for Dermabond Advanced.

- 
- Anticipated: an effect which by its nature, incidence, severity or outcome has been previously identified in applicable product information (risk analysis report, Instruction for use).

## 9.3.2 Safety Reporting

### 9.3.2.1 Documentation and Reporting of Adverse Events

Adverse events should be reported and documented in accordance with the procedures outlined below. All AEs occurring during the study must be documented on the relevant eCRF pages. The following data should be documented for each AE:

- Description of the symptom event
- Classification of ‘serious’ or ‘not serious’
- Severity
- Date of first occurrence and date of resolution (if applicable)
- Action taken
- Causal relationship
- Outcome of event (unknown, recovered, not yet recovered, recovered with sequelae, death [with date and cause reported])

The investigator will record all AEs from the time following the signature of informed consent/assent until the last visit of the subject or later in case of ongoing AEs.

It is the responsibility of the investigator to document all AEs that occur during the study. Adverse events may be directly observed, evident in laboratory or diagnostic results, reported spontaneously by the subject, or by questioning the subject at each study visit. Subjects should be questioned in a general way, without directly prompting about the occurrence of any specific symptoms (eg, “How have you been feeling since the last visit?”). Adverse events should be reported on the appropriate page of the eCRF.

### 9.3.2.2 Reporting of Serious Adverse Events

From the signature of informed consent/assent until the last visit of the subject, the investigator must notify Syneos Health of the following events immediately (within 24 hours of the investigator becoming aware of the event) regardless of their causality:

- Any SAE
- Any DD
- New findings/updates in relation to already reported events

Serious AEs occurring in or to subjects that are in the comparator arm of an investigation shall also be reported in accordance with the SAE reporting system.

This initial notification is the object of the SAE/DD form reported by e-mail or by fax (see Section 15.8). The investigator will be requested to supply as much detailed information regarding the event that is available at the time of the initial contact (examinations carried out, laboratory results, etc.).

---

The investigator is also required to submit follow-up reports as soon as possible, including additional information such as diagnosis, outcome, causality assessment, results of specific investigations, and any new significant information that has not been previously reported.

Copies of additional laboratory tests, consultation reports, post mortem reports, hospital case reports, autopsy reports, and other documents should be sent when requested and applicable.

Instances of death, congenital abnormality, or an event that is of such clinical concern as to influence the overall assessment of safety, if brought to the attention of the investigator at any time after cessation of study device administration and linked by the investigator to this study, should be reported to the study monitor. The sponsor and/or Syneos Health will promptly notify all relevant safety information to the competent authorities, central Ethics Committees and investigators according to the local, national specific, safety reporting requirements and timelines in compliance with the required deadlines, and in accordance with European Union medical device directives and medical device guidelines: MEDDEV 2.7/3 rev 3. The same notification process and reporting timelines will apply for all products involved in the study. This also applies to the reporting of any new safety information which may modify significantly the benefit risk ratio of an investigational product or which may lead to modification of the conditions of use of the investigational product.

Details of the procedures to be followed if a pregnancy occurs are provided in Section 7.3.4.

### **9.3.2.3 Follow-up of Adverse Events**

All investigators should follow-up with subjects with AEs/ADEs/SAEs until the event is resolved or until, in the opinion of the investigator, the event is stabilized or determined to be chronic. Details of AE resolution must be documented in the eCRF. If the AE extends beyond the end of the study, it will be followed until resolution although the study will proceed with close-out activities independently.

Subjects should be followed-up by the end of study visit (Month 3/Early Discontinuation), and any AEs/ADEs/SAEs/DDs that occur during this time should be reported according to the procedures outlined above.

For all SAEs, where important or relevant information is missing, active follow-up should be undertaken. The subject must be followed-up until clinical recovery is complete and laboratory results have returned to normal, or until progression has been stabilized or until the last study visit, whichever comes first. This information should be documented in the subject's medical records.

## **9.3.3 AE Assessments**

### **9.3.3.1 Assessment of Severity**

Each AE will be assigned a category by the investigator as follows:

- Mild: An AE that is easily tolerated by the subject, causes minimal discomfort and does not interfere with everyday activities.
- Moderate: An AE that is sufficiently discomforting to interfere with normal everyday activities; intervention may be needed.

---

**Severe:** An AE that prevents normal everyday activities; treatment or other intervention usually needed.

The most severe manifestation will be used for the final AE characterization. It will be recorded as the same AE.

### 9.3.3.2 Assessment of Causality

Every effort will be made by the investigator to assess the relationship of the AE, if any, to the IMD. Causality should be assessed using the categories presented in the following table:

Unrelated:	Clinical event with an incompatible time relationship to IMD use, and that could be explained by underlying disease or other drugs or chemicals or is incontrovertibly not related to the IMD.
Unlikely:	Clinical event whose time relationship to IMD use makes a causal connection improbable, but that could plausibly be explained by underlying disease or other drugs or chemicals.
Possible:	Clinical event with a reasonable time relationship to IMD use, but that could also be explained by concurrent disease or other drugs or chemicals.
Probable:	Clinical event with a reasonable time relationship to IMD use, and is unlikely to be attributed to concurrent disease or other drugs or chemicals.
Very Likely/Certain:	Clinical event with plausible time relationship to IMD use, and that cannot be explained by concurrent disease or other drugs or chemicals.

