The risk is also greater with smoking, obesity, premature postsurgery exercise, heavy lifting, recurrent vomiting, coughing, or an improper diet that leads to constipation.

Any wound dehiscence needs to be treated as a new wound and is a surgical emergency that requires immediate attention. Surgical debridements, antibiotic therapy, reclosure with the appropriate surgical technique, and sutures represent the most appropriate treatments. Finally, the patient's wound should be closely monitored to prevent dehiscence from recurring.

For all the above mentioned reasons, wound dehiscence always needs to be prevented as much as possible.

Therefore, a new, polyurethane-based topical skin adhesive has been developed: MAR-CUTIS. MAR-CUTIS is intended for topical application to close wounds of the skin, such as cuts and wounds from surgical incisions. It consists of a polyurethane-based prepolymer and an amino acid-based hardening agent which are provided in prefilled, double syringes with a mixing cannula and spreader tip.

Information about the preclinical testing as well as known and expected benefits, risks, serious adverse events (SAEs) and reasonably anticipated adverse events (AEs) of MAR-CUTIS are to be found in the Investigator's Brochure.

In particular, there are some predictable AEs (rates) that have been observed with other skin adhesives and can be possibly associated with the use of MAR-CUTIS:

- Infection (3.6%) after wound closure; this also applies to sutures and is not limited to adhesives.
- Dehiscence (2.5%) which is greater in wounds closed with skin adhesive as compared to other methods of wound closure (namely sutures, staples and strips).
- Improper application of the skin adhesive (unknown).

- Allergic reactions (11.5%).
- Other additional risks mentioned in risk management file, eg, pain (6.1%), edema (9.7%), and warmth (1.3%).

Such novel polyurethane-based medical adhesive differs from existing technologies due to its unique composition. The adhesive technology is:

- Fully Synthetic
- Easy to use
- Flexible

Based on polyurethane, it is completely different from existing skin adhesives based on cyanoacrylate. This new component is adhering to the tissue via mechanical and physical adhesion, forming a strong, yet flexible film. There is no reaction with the tissue itself; a strong polymer network is quickly formed and full polymerization is completed after a few minutes.

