14.1 Adverse events

A treatment emergent adverse event (TEAE) is defined as any adverse event that, based on start date information, occurs in the on-treatment-period as defined in Section 8.2.2. This includes any events related to the procedures, the IMD, or the comparator.

A pre-treatment non-TEAE is an adverse event starting in the pre-treatment period as defined in Section 8.2.2.

A serious adverse event (SAE) is any untoward medical occurrence of effect that:

- Led to death, or
- Led to serious deterioration in the health of the subject, or
- Led to fetal distress, fetal death, or a congenital abnormality or birth defect.

This includes device deficiencies that might have led to a SAE. More details on the definition of SAEs are available in Protocol Section 9.3.1.

If there are partial dates or times, an adverse event will be considered treatment emergent unless the information available will clearly exclude it. Further details can be found in Section 16.1.4.1.

Assignment of TEAEs to treatment will be based on the definition of the on-treatment-period given in Section 8.2.2, thus, TEAEs occurring during the on-treatment period are assigned to the respective treatment.

The causal relationship of TEAEs to IMD is categorized as follows:

Category	Assessment by investigator
Related	probable certain/very likely possible
Not related	unlikely unrelated

An Adverse Device Effect (ADE) is an AE related to the use of an IMD. This includes any AE resulting from insufficiencies or inadequacies in the instructions for use, deployment, implantation, installation, operation or any malfunction of the IMD. ADEs are a subset of TEAEs.

An ADE that results in any of the consequences characteristic of a SAE will be considered as a serious ADE.

Serious ADEs which by its nature, incidence, severity or outcome have not been identified in the current version of the MAR-CUTIS risk analysis report or Instructions for use for Dermabond Advance (see Protocol Section 15.2 for more details) will be considered as unanticipated ADEs. Anticipated ADAs are defined as events that have been previously identified in applicable product information.

The following overview tables will be generated by treatment group and overall.

1. Summary of the number and percentage of subjects with at least 1 of the following events, and of summary of the number and percentage of TEAEs for:
 - TEAEs.
 - Serious TEAEs.
 - Non-serious TEAEs.
 - TEAEs leading to withdrawal from the trial.
 - ADEs.

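### The causality scale does not name the operation or injury as another cause, and relatedness is recorded to the adhesive only, so ADE counts can mix device effects with procedural wound reactions

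*Protocol*

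**What the plan says.** The main safety endpoint (protocol Section 6) is adverse events within one month, classified by severity and by relatedness to treatment. Relatedness is the investigator's grade on the five-level table in protocol 9.3.3.2:

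- *Possible* is defined as a "Clinical event with a reasonable time relationship to IMD use, but that could also be explained by concurrent disease or other drugs or chemicals"; surgery and injury are not listed.
- *Probable* is defined as a "Clinical event with a reasonable time relationship to IMD use, and is unlikely to be attributed to concurrent disease or other drugs or chemicals"; here too, surgery and injury are not listed.
- *Very Likely/Certain* needs plausible timing, for an event "that cannot be explained by concurrent disease or other drugs or chemicals".
- *Unlikely* is defined as a "Clinical event whose time relationship to IMD use makes a causal connection improbable", with disease, drugs or chemicals as a plausible explanation.
- *Unrelated* needs incompatible timing together with one of the same explanations, "or is incontrovertibly not related to the IMD".

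The AE definition in protocol 9.3.1 is wider than this scale. It states: "This includes events related to the procedures involved (any procedure in the clinical investigation plan"). The TEAE definition in SAP 14.1 also takes in events related to the procedures. Yet the data items in protocol 9.3.2.1 list one causal relationship, and 9.3.3.2 defines it with respect to the IMD. Neither document describes a field or table for relationship to the procedure.

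SAP 14.1 reduces the five grades to two. Related is "probable certain/very likely possible"; the other two grades are not related. ADEs are AEs related to use of the device, and they feed the ADE, serious ADE and anticipated/unanticipated ADE tables in SAP 14.1 and 14.1.1.

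**The concern.** Every subject has had an incision or a trauma at the glued site shortly before the adhesive goes on, and deep layers are closed first where needed (protocol 7.4.4). The protocol's own Introduction treats the surgical procedure as one of the two most important influences on dehiscence risk and says that infection is not limited to adhesives. For local pain, edema, redness or warmth, the procedure or injury is an obvious competing cause, and the scale does not name it.

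Two things are at stake. First, if procedural reactions are counted as ADEs in both arms, the ADE rates contain a shared background that pulls their ratio towards 1. Second, some investigators will read surgery into underlying or concurrent disease and others will apply the table as written. With up to 22 centers and open-label assessment, the same event could be coded differently by site, and possibly by arm.

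**Working it through.** No figure in the plan is in dispute, so the check is mainly of text.

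**Step 1: grade one event.** Take wound edema on Day 1, recorded as an AE, in an otherwise healthy subject after a laparotomy.

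| Grade | Condition | Met on a literal reading? |
|---|---|---|
| Unrelated | Incompatible timing plus another explanation, or incontrovertibly not the device | No on timing; the second route is very hard to establish at the glued wound |
| Unlikely | Timing makes a causal link improbable | No |
| Possible | Reasonable timing; disease, drug or chemical could explain it | No; none is present |
| Probable | Reasonable timing; those three unlikely | Yes |
| Very Likely/Certain | Plausible timing; those three cannot explain it | Arguably |

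The event grades *Probable* or higher, SAP 14.1 makes it Related, and it enters the ADE tables.

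**Step 2: add the operation and injury to the list of causes and change nothing else.** The edema now has a named alternative and moves to *Possible*. It cannot reach *Unlikely*, because the timing condition still fails. SAP 14.1 counts *Possible* as Related, so the ADE count is unchanged. The SAP tabulates intensity, outcome and action taken, but lists no table by the five-level grade, so the shift would not show in the summaries. The reported count is driven by the timing condition in *Unlikely* together with the pooling of *Possible*.

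**Step 3: illustrate dilution.** These rates are assumptions; the documents give none for this purpose. Let adhesive-caused events occur in a = 10% (MAR-CUTIS) and 5% (Dermabond Advanced). Let procedural reactions occur independently in s of both arms, all recorded as AEs and all classed as related. The ADE rate is 1 − (1 − a)(1 − s). For s = 10%: 1 − 0.90 × 0.90 = 19.0% and 1 − 0.95 × 0.90 = 14.5%. The last column is the chance that the observed ratio is at least 1.5, by full binomial enumeration with the planned 126 and 63 subjects. A comparator count of zero is taken as meeting the criterion when s = 0.

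| s | ADE rates | Ratio | Difference (points) | Chance of observed ratio ≥ 1.5 |
|---|---|---|---|---|
| 0% | 10.0% vs 5.0% | 2.00 | 5.0 | 73% |
| 10% | 19.0% vs 14.5% | 1.31 | 4.5 | 39% |
| 20% | 28.0% vs 24.0% | 1.17 | 4.0 | 20% |
| 40% | 46.0% vs 43.0% | 1.07 | 3.0 | 4% |

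The 1.5 threshold is also an illustration; neither document uses it.

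**Step 4: what the documents offer for scale.** The Introduction gives rates seen with other skin adhesives: pain 6.1%, edema 9.7%, warmth 1.3%. Together they affect between 9.7% of subjects (complete overlap) and 6.1 + 9.7 + 1.3 = 17.1% (no overlap). That is 12.2 to 21.5 of 126 and 6.1 to 10.8 of 63. The other listed events with a rate are infection 3.6%, dehiscence 2.5% and allergic reactions 11.5%, which sum to 17.6%. The three wound reactions are then 9.7/(9.7 + 17.6) = 36% to 17.1/(17.1 + 17.6) = 49% of the listed total. These rates describe wounds closed with adhesive, so they are not a background rate for surgery alone.

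**The case against.** A reader might infer that the table accepts nothing but disease, drugs or chemicals, that ordinary healing signs become device effects by rule, and that they swamp the safety endpoint. The documents do not support this.

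- *Unrelated* has an open exit that is not tied to those three causes. This stands, although the bar is very high for pain or redness under the glue.
- The grade is the investigator's judgement, and underlying or concurrent disease could be read to include the injury or the condition operated on. This stands against any claim of a fixed rule. It also means that readings can differ.
- Not every healing sign must be an AE. Protocol 9.3.1 exempts anticipated fluctuations of pre-existing conditions, including the disease under study, without clinically significant worsening. Erythema, edema, pain at rest and local temperature also have their own items in the wound infection score. How far the exemption reaches signs after an elective incision is unclear, but the assumption in Step 3 that every reaction is recorded is an upper case.
- No document figure shows that procedural reactions dominate. On the difference scale the loss is modest at the lower assumed backgrounds (5.0 to 4.5 or 4.0 points).
- The same scale applies to both arms, so an equal background creates no spurious difference, and over-attribution is conservative for each device's absolute ADE rate. This stands.
- Safety is descriptive, and TEAEs are tabulated regardless of causality, so local events can be compared without the relatedness filter. This limits the harm, but those tables cannot show which Related events were thought procedural.

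**Conclusion.** The concern holds in a limited form. The causality table does not name the operation, injury or deep closure, and relatedness is recorded once, to the device, although the AE and TEAE definitions include procedure-related events. On a literal reading, early local reactions that are recorded as AEs and not otherwise explained count as ADEs in both arms. This can dilute a real difference and allows inconsistent coding between sites.

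The size is unknown. The ratios of 1.31 to 1.07 rest on assumed adhesive rates, an assumed equal and independent background, and the assumption that every such reaction is recorded and classed as related. Variation between sites is a risk that the wording creates; nothing in the documents shows how large it would be. The point does not touch the primary endpoint or the sample size. It is worth acting on because the remedy is cheap and changes what the safety tables can tell a reader.

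**What to change.** 1. **eCRF and protocol 9.3.2.1:** add a separate field for relationship to the surgical procedure, injury or wound care, alongside the existing relationship to the IMD.
2. **SAP 14.1:** add an overview line for procedure-related TEAEs, and show ADEs split by whether the event is also judged procedure-related. Keep the existing ADE definition as the main table.
3. **Protocol 9.3.3.2:** name the procedure and injury as alternative causes, and let an event judged mainly procedural be graded *Unlikely* without requiring improbable timing. Without that second change, or the split in item 2, the rewording only moves events from *Probable* to *Possible* and leaves the Related count as it was.

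The cost is one eCRF field, revised wording in one table, and one SAP line with a split of an existing table. The downside is one more investigator judgement in an open-label trial.
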